12.4.1.1 Statistical Hypotheses

The null and alternative hypotheses are formulated in terms of the predefined margin of 0.10 (in logMAR scale) for noninferiority:

$$H_0: \mu_{(T)} - \mu_{(C)} \geq 0.10$$

$$H_a: \mu_{(T)} - \mu_{(C)} < 0.10$$

where $\mu_{(T)}$ and $\mu_{(C)}$ denote the Week 1 Follow-up mean CLCDVA for [REDACTED] and Biofinity contact lenses, respectively, on the logMAR scale.

12.4.1.2 Analysis Methods

A mixed effects repeated measures model will be utilized to test these hypotheses. The model will include terms for lens, visit (Dispense, Week 1 Follow-up, Month 1 Follow-up, and Month 3 Follow-up), and lens-by-visit interaction as fixed effects. [REDACTED]

[REDACTED] Within-subject correlation due to eye will also be accounted for in the model. Lens difference ([REDACTED] minus Biofinity) and the corresponding two-sided 95% CI will be computed for 1-Week Follow-up. Noninferiority in CLCDVA will be declared if the upper confidence limit is less than 0.10.

12.4.2 Analysis of Secondary Effectiveness Endpoints

The secondary effectiveness objective is to demonstrate noninferiority of [REDACTED] compared to Biofinity in the percentage of subjects achieving distance VA 20/20 or better, in each eye, at Week 1 Follow-up.

The corresponding endpoint is the percentage (proportion) of subjects with CLCDVA of 20/20 or better, measured monocularly, in both OD and OS at Week 1 Follow-up.

12.4.2.1 Statistical Hypotheses

The null and alternative hypotheses are formulated in terms of the predefined margin of 0.10 (10%) for noninferiority.

$$H_0: P_{(T)} - P_{(C)} \leq -0.10$$

$$H_a: P_{(T)} - P_{(C)} > -0.10$$

where $P_{(T)}$ and $P_{(C)}$ denote the proportion of subjects attaining at least 20/20 in CLCDVA at Week 1 Follow-up in each eye (OD and OS) for [REDACTED] and Biofinity contact lenses, respectively.

12.6 Safety Analyses

The safety endpoints are:

- AEs
- Biomicroscopy Findings
- Device Deficiencies

There are no safety hypotheses planned in this study. The focus of the safety analysis will be a comprehensive descriptive assessment of occurrence of AE as well as the other listed parameters.

All AEs occurring from the time a subject signs informed consent to study exit will be accounted for in the reporting. Safety analyses will be conducted using the safety analysis set on a treatment-emergent basis. Descriptive summaries (counts and percentages) for ocular and nonocular AEs will be presented by Medical Dictionary for Regulatory Activities Preferred Terms. AEs leading to study discontinuation, significant non-serious AEs, and SAEs will be identified. Individual subject listings will be provided, as necessary.

Individual subject listings will be provided for AEs that occur after signing informed consent but prior to exposure to IP.

Two listings for device deficiencies, prior to exposure of study contact lenses and treatment-emergent, will be provided. Additionally, each device deficiency category will be tabulated.

No inferential testing will be done for safety analysis.

[REDACTED]

[REDACTED]

[REDACTED]

[REDACTED]

[REDACTED]

[REDACTED]

[REDACTED]

[REDACTED]

| [REDACTED]

| [REDACTED]

13 DATA HANDLING AND ADMINISTRATIVE REQUIREMENTS

13.1 Subject Confidentiality

The Investigator must ensure that the subject's anonymity is maintained throughout the course of the study. In particular, the Investigator must keep an enrollment log with confidential identifying information that corresponds to the subject numbers and initials of each study participant. [REDACTED]

[REDACTED] . [REDACTED]

13.2 Completion of Source Documents and Case Report Forms

The nature and location of all source documents will be identified to ensure that original data required to complete the CRFs exist and are accessible for verification by the site monitor, and all discrepancies shall be appropriately documented via the query resolution process. Site monitors are appointed by the Study Sponsor and are independent of study site staff.

A large black rectangular redaction box covers the top portion of the page, from approximately the top third to the middle. A smaller black rectangular redaction box is located in the bottom left corner.

13.3 Data Review and Clarifications

A review of CRF data to the subject's source data will be completed by the site monitor to ensure completeness and accuracy. After the CRFs have been completed, additional data clarifications and/or additions may be needed as a result of the data cleaning process. Data clarifications are documented and are part of each subject's CRF.

13.4 Sponsor and Monitoring Responsibilities

The Study Sponsor will designate a monitor to conduct the appropriate site visits at the appropriate intervals according to the study monitoring plan. The clinical investigation will be monitored to ensure that the rights and well-being of the subjects are protected, the reported data are accurate, complete, and verifiable from the source documents, and the study is conducted in compliance with the current approved protocol (and amendments[s], if applicable), with current GCP, and with applicable regulatory requirements.

The site may not screen subjects or perform the informed consent process on any subject until it receives a notification from an appropriate Study Sponsor representative that the site may commence conducting study activities. Monitoring will be conducted periodically while the clinical study is ongoing. Monitoring methods may include site visits, telephone, written and fax correspondence. Close-out visits will take place after the last visit of the last subject at the site.

A Coordinating Investigator may be identified by the Study Sponsor to review and endorse the final study report. In cases where a Coordinating Investigator is engaged, the Study Sponsor will select the Coordinating Investigator based upon their experience, qualifications, active study participation, and their willingness and availability to take on this role.

13.5 Regulatory Documentation and Records Retention

The Investigator is required to maintain up-to-date, complete regulatory documentation as indicated by the Study Sponsor and the Investigator's files will be reviewed as part of the ongoing study monitoring. [REDACTED]

[REDACTED]

[REDACTED]

[REDACTED]

[REDACTED]

[REDACTED]

13.6 Quality Assurance and Quality Control

The Study Sponsor will secure agreement from all involved parties to ensure direct access to all study related sites, source data and documents, and reports for the purpose of monitoring and auditing by the Study Sponsor, and inspection by domestic and foreign regulatory authorities. Quality control will be applied to each stage of data handling to ensure that all data are reliable and have been processed correctly. Agreements made by the Study Sponsor with the Investigator/Institution and any other parties involved in the clinical study will be provided in writing as part of the protocol or as a separate agreement.

14 ETHICS

[REDACTED]

[REDACTED]

[REDACTED]

[REDACTED]

[REDACTED]

[REDACTED]

The Investigator must ensure that all personnel involved in the conduct of the study are qualified to perform their assigned responsibilities through relevant education, training, and experience. The Investigator and all clinical study staff must conduct the clinical study in compliance with the protocol. Deviations from this protocol, regulatory requirements and/or GCP must be recorded and reported to the Sponsor prior to database lock. If needed,

corrective and preventive action should be identified, implemented, and documented within the study records. Use of waivers to deviate from the clinical protocol is prohibited.

Before clinical study initiation, this protocol, the informed consent form, any other written information given to subjects, and any advertisements planned for subject recruitment must be approved by an IRB/IEC. [REDACTED]

[REDACTED]

[REDACTED]

[REDACTED]

[REDACTED]

[REDACTED]

[REDACTED]

[REDACTED]

Voluntary informed consent must be obtained in writing from every subject and the process shall be documented before any procedure specific to the clinical investigation is applied to the subject. The Investigator must have a defined process for obtaining consent. [REDACTED]

The Study Sponsor assures that the key design elements of this protocol will be registered on www.clinicaltrials.gov as required by current regulations and, if applicable, other public databases as required by local country regulations. In addition, results of this study will be

made publicly available on www.clinicaltrials.gov regardless of outcome as required by current regulations and, if applicable, in other public databases as required by local country regulations.

[figure not shown]
10.1007/s00332-010-9000-0

1 | Page

■ [REDACTED]

— [REDACTED]

11. **What is the primary purpose of the study?** (check all that apply)

[figure not shown]
—  —

© 2013 Pearson Education, Inc.

[figure not shown]
I [REDACTED]

For more information, contact the Office of the Vice President for Research and Economic Development at [contact] or [contact].

1000

Signature Page for V-CLN-0000052 v1.0

Signature Page for V-CLN-0000052 v1.0

**Job Notes:**

This is the first revision (Version 2.0) of the Statistical Analysis Plan for this study. This version of the Statistical Analysis Plan is based on Version 1.0 of the study protocol.

**Executive Summary:**

**Key Objective:**

The primary effectiveness objective is to demonstrate noninferiority of [REDACTED] soft contact lenses ([REDACTED] compared to BIOFINITY® soft contact lenses (Biofinity), in contact lens corrected distance visual acuity (CLCDVA) at Week 1 Follow-up.

The secondary effectiveness objective is to demonstrate noninferiority of [REDACTED] compared to Biofinity in the percentage of subjects achieving CLCDVA 20/20 or better, in each eye, at Week 1 Follow-up.

[REDACTED] :

[REDACTED]  
[REDACTED]

[REDACTED]  
[REDACTED]

## 1 STUDY OBJECTIVES AND DESIGN

To address the primary and secondary effectiveness objectives, data from a pre-determined subset of subjects from CLY935-C010 will be combined with data from the current study, and all planned analyses will be performed on the combined set of data.

### 1.1 Study Objectives

#### PRIMARY OBJECTIVE

The primary effectiveness objective is to demonstrate noninferiority of [REDACTED] compared to Biofinity in mean CLCDVA at Week 1 Follow-up.

#### SECONDARY OBJECTIVE

The secondary effectiveness objective is to demonstrate noninferiority of [REDACTED] compared to Biofinity in the percentage of subjects achieving CLCDVA 20/20 or better, in each eye, at Week 1 Follow-up.

### 1.2 Study Description

Key components of the study are summarized in Table 1-1.

**Table 1-1** **Study Description Summary**

Study Design	Prospective, multi-center, randomized, [REDACTED] [REDACTED] controlled, double-masked, parallel-group.
Study Population	Volunteer subjects aged 18 or over who are adapted daily wear frequent replacement soft contact lens wearers, excluding Biofinity habitual wearers, have at least 3 months of soft contact lens wearing experience, and who wear their habitual lenses at least 5 days per week and at least 8 hours per day.  [REDACTED] [REDACTED] [REDACTED] [REDACTED] Target to complete: 120 subjects (80 Test: 40 Control). [REDACTED]

	
Planned: ~160 subjects enrolled, ~144 subjects randomized (96 Test: 48 Control)

Number of Sites	~16 (US)
Test Product	██████ soft contact lens ████████
Control Product	CooperVision® BIOFINITY® (comfilcon A) contact lens (Biofinity)
Planned Duration of Exposure	~ 3 months
Visits	
Visit 1: Screening/Baseline/Dispense (Day 1)
 
Visit 2: Week 1 Follow-up ████████
 
Visit 3: Month 1 Follow-up ████████
 
Visit 4: Month 3 Follow-up/Exit ████████

### 1.3 Randomization

A member of the Randomization Programming group at Alcon who is not part of the study team will generate the randomized allocation schedule(s) for study lens assignment.

Subjects will be randomized in a 2:1 ratio to receive either [REDACTED] or Biofinity contact lenses, respectively. [REDACTED]

## 1.4 Masking

This study is double-masked.

[REDACTED]

[REDACTED]

[REDACTED]

[REDACTED]

[REDACTED]

[REDACTED]

[REDACTED]

## 2 ANALYSIS SETS

Data from a subset of subjects in the CLY935-C010 study will be combined with data from this study. This combined set will serve as the basis for all planned analyses for the primary and secondary effectiveness objectives. [REDACTED]. Subjects in CLY935-C010 will be included in the combined set only if they satisfy the following criterion:

- Best corrected visual acuity (BCVA) of 20/20 or better in each eye at the Screening/Baseline/Dispense Visit

### 2.1 Safety Analysis Set

Safety analyses will be conducted using the safety analysis set on a treatment-emergent basis. As such, the safety analysis set will include all subjects/eyes exposed to any study lenses evaluated in this study. [REDACTED]

[REDACTED]. For treatment-emergent safety analyses, subjects/eyes will be categorized under the actual study lenses exposed.

### 2.2 Full Analysis Set

The full analysis set (FAS) is the set of all randomized subjects who are exposed to any study lenses evaluated in this study, [REDACTED] and who have at least one post-baseline (post-Dispense) CLCDVA.

### 2.3 Per Protocol Analysis Set

The per protocol (PP) analysis set is a subset of FAS and excludes all data/subjects that have met any of the critical deviation or evaluability criteria identified in the Deviations and Evaluability Plan (DEP).

### 3 SUBJECT CHARACTERISTICS AND STUDY CONDUCT SUMMARIES

Demographic information (age, sex, ethnicity, and race), recent lens-wearing experience (wear modality, wear success), and habitual lens information will be presented by lens group and overall for the safety, full, and per protocol analysis sets.

Baseline data will also be summarized by lens group and overall on the safety, full and per protocol analysis sets.

- [REDACTED]

### 4 EFFECTIVENESS ANALYSIS STRATEGY

This study defines 1 primary, 1 secondary [REDACTED] effectiveness endpoints.

[REDACTED]  
[REDACTED]. Primary inference will be done on the PP analysis set. [REDACTED]

- [REDACTED]
- [REDACTED]
- [REDACTED]
- [REDACTED]
- [REDACTED].

- [REDACTED]
- [REDACTED]

All data obtained in evaluable subjects/eyes will be included in the analysis. No imputation for missing values will be carried out for the effectiveness analyses.

[figure not shown]

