3 PROTOCOL SUMMARY

This will be a prospective, randomized, [REDACTED] controlled, double-masked, parallel-group daily wear clinical study.

Approximately 16 sites in the US will enroll approximately 160 subjects. Subjects will be expected to attend 4 office visits: Screening/Baseline/Dispense, Week 1 Follow-up, Month 1 Follow-up, and Month 3 Follow-up/Exit. The total expected duration of participation for each subject is approximately 3-4 months in this daily wear clinical study. Accounting for both screen failure and dropout rates, approximately 96 subjects will be assigned to wear the test lenses and 48 subjects will be assigned to wear the control lenses, [REDACTED]

[REDACTED]
[REDACTED].

[REDACTED]
[REDACTED]
[REDACTED]
[REDACTED]
[REDACTED].

Subjects and the study personnel conducting the study evaluations will be masked to treatment. Subjects who meet the inclusion and exclusion criteria will be randomized to wear either the test contact lenses [REDACTED] in both eyes or the control contact lenses (Biofinity) in both eyes for 3 months of daily wear exposure.

[REDACTED]
[REDACTED]
[REDACTED]
[REDACTED]
[REDACTED]
[REDACTED]
[REDACTED]
[REDACTED].

At the Screening/Baseline/Dispense Visit, study lenses will be dispensed to qualified subjects [REDACTED]

[REDACTED] All study lenses will be worn for at least 5 days per week and 8 hours per day in a daily wear modality (eg, will not be worn while sleeping). [REDACTED]

[REDACTED]

[REDACTED]

[REDACTED]. Regardless of whether the subject is randomized to the test or the control group, CLEAR CARE Cleaning & Disinfecting Solution (CLEAR CARE) must be used for cleaning and disinfection. [REDACTED]

Investigational product type	Medical Device
Study type	Interventional
Investigational products	Test Product: [REDACTED] soft contact lens Control Product: Biofinity soft contact lens
Purpose and rationale	The purpose of this clinical study is to evaluate the safety and performance of the investigational [REDACTED] soft contact lens compared to the commercially available Biofinity soft contact lens, when worn in a daily wear modality, by assessing visual acuity as the primary endpoint.

	
■ [REDACTED]
 
Safety
 
 • AEs • Biomicroscopy • Device deficiencies

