12.1 Subject Evaluability

Final subject evaluability must be determined prior to breaking the code for masked treatment (lens) assignment and locking the database, [REDACTED]

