## 4.3 Statistical Methods for Effectiveness Analyses

### 4.3.1 Primary Effectiveness Analyses

A mixed effects repeated measures model will be utilized to test these hypotheses. [REDACTED]

[REDACTED]

[REDACTED]. Lens difference ([REDACTED] minus Biofinity) and the corresponding two-sided 95% CI will be computed for Week 1 Follow-up. Noninferiority in CLCDVA will be declared if the upper confidence limit is less than 0.10.

[REDACTED]

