### 4.3.2 Secondary Effectiveness Analyses

[REDACTED]

[REDACTED]

From the two-sided 95% CI on the lens difference ( [redacted] minus Biofinity), noninferiority in proportion of subjects achieving 20/20 or better in CLCDVA in both eyes will be declared if the lower confidence limit is greater than -0.10.

A series of horizontal black bars of varying lengths, likely representing data points or measurements. The bars are arranged in a grid-like pattern with some vertical alignment. The lengths of the bars vary significantly, with some being very short and others extending almost to the top of the frame. The bars are positioned in rows, with some rows having a single bar and others having multiple bars. The overall pattern suggests a data visualization or a series of measurements taken at different times or locations.

[REDACTED]

[REDACTED]

[REDACTED]

[REDACTED]

[REDACTED]

[REDACTED]

[REDACTED]

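### Primary inference rests on the per-protocol set, and no visible text requires the full analysis set to agree before noninferiority is claimed

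*SAP*

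**What the plan says.** SAP section 4 (Effectiveness Analysis Strategy) puts the decision on the per-protocol (PP) set: "Primary inference will be done on the PP analysis set". The sentence is not limited to one endpoint, and the section covers both the primary and the secondary effectiveness endpoint. Text before and after it is redacted, as is text in the matching protocol section 12.4.

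SAP section 2.3 makes PP a subset of the FAS that "excludes all data/subjects that have met any of the critical deviation or evaluability criteria identified in the Deviations and Evaluability Plan". That plan (the DEP) is not among the documents. The FAS is defined in SAP section 2.2: "The full analysis set (FAS) is the set of all randomized subjects who are exposed to any study lenses evaluated in this study", with the further condition of a CLCDVA reading after dispensing. SAP section 4 rules out imputation.

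The success rules name a confidence limit but no analysis set. For the primary endpoint, SAP section 4.3.1 has "Noninferiority in CLCDVA will be declared if the upper confidence limit is less than 0.10". For the 20/20 responder endpoint, SAP section 4.3.2 says that noninferiority "will be declared if the lower confidence limit is greater than -0.10".

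Two safeguards are visible. Protocol section 12.1 says "Final subject evaluability must be determined prior to breaking the code for masked treatment (lens) assignment and locking the database", and protocol section 3 says "Subjects and the study personnel conducting the study evaluations will be masked to treatment".

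**The concern.** PP membership is settled after randomisation. If a deviation or evaluability criterion can be triggered by how well the lens performs, the PP comparison no longer follows the randomised groups. In a noninferiority trial the direction matters. When the test lens is truly worse it produces more failures, so a criterion that catches failures removes more subjects from the test arm and shrinks the observed difference. Neither PP nor FAS is reliably conservative here, and agreement between them is the usual protection. The visible text does not ask for it. At stake is a false claim, most plainly on the 20/20 endpoint, where a handful of subjects can move the confidence limit across -0.10.

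**Working it through.** **Plan figures.** SAP Table 1-1 gives about 144 randomised (96:48) and a target of 120 completers (80:40). These are consistent: both are 2:1, and 1 - 120/144 = 16.7% loss. The two-sided 95% interval gives a nominal one-sided error of 0.025. The plan shows no PP exclusion rate, control 20/20 rate or SD, and no size for the CLY935-C010 subset, so these are assumptions below.

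**Set-up for the secondary endpoint.** The control rate is pC = 0.90 or 0.95, and the test rate is pT = pC - 0.10, exactly at the margin. The lower limit is Newcombe's, L = d - sqrt[(pT - lT)² + (uC - pC)²], computed from the observed rates, where d is the test-minus-control difference and lT and uC are Wilson limits. Noninferiority is declared if L > -0.10. There were 200,000 runs per case. Newcombe stands in for the planned generalized linear mixed model, whose details are redacted.

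**Step 1: why a lens-blind rule still biases.** If a fraction f of failures is excluded in each arm, the expected PP rate is p/[1 - f(1 - p)]. With pC = 0.90, pT = 0.80 and f = 0.20:
- control: 0.90/0.98 = 0.918
- test: 0.80/0.96 = 0.833
- PP difference: -0.085, against a true -0.10

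The expected exclusions are few: 0.20 × 96 × 0.20 = 3.8 test subjects and 0.20 × 48 × 0.10 = 1.0 control subject.

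**Step 2: false noninferiority rate at 96:48, over both control rates.**

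| Failures excluded | Equally in both arms | Test arm only (worst case) |
|---|---|---|
| 0% | 2.7% | 2.7% |
| 10% | about 4% | about 5% |
| 20% | 5-6% | about 9% |
| 30% | 7-9% | 15-16% |

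If the CLY935-C010 subset doubled the size to 192:96 (assumed), the rate with equal exclusion would rise from 2.8% to between about 4% and 14.5%. In the test-only worst case it would reach about 7%, 14% and 26-27%.

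**Step 3: primary endpoint, worst case only.** The true difference is 0.10 logMAR, SD 0.06 to 0.12 (assumed), with one value per subject and a pooled t interval. Removing the worst 2, 5 or 10 of 96 test-lens subjects raises the error from about 0.025 to about 0.05, 0.11 and 0.25. Loss to 80:40 unrelated to outcome leaves it at about 0.025. The equal-exclusion case was not run for this endpoint.

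**Step 4: does requiring both sets help?** Here the FAS keeps the measured failures that PP drops. Declaring noninferiority only when both sets meet the margin held the secondary false noninferiority rate at 2.2-2.8% in every scenario of step 2.

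**The case against.** The strongest reply is that the plan may already contain the remedy. Redactions surround the quoted sentence, and the hidden text could state a joint PP and FAS requirement or a rule for disagreement. A reader might infer that PP decides by itself and that a PP success stands even if the FAS fails. The documents do not support that, because no sentence says it and redacted text is not missing text. This objection stands, and it is why the request is to state or confirm.

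The second reply is masking. Evaluability is final before the code is broken, so a reader who infers that poorly performing test-lens subjects could be picked out by assignment goes too far. This also stands. It does not close the indirect route of a masked criterion that poor vision can trigger.

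Third, the DEP is unseen. Low wear, missed visits or lens changes are possible criteria, not documented ones. The endpoint is at Day 8 and PP can drop data as well as subjects, so later non-compliance need not touch the Week 1 value. That makes the size uncertain but does not remove the mechanism.

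Fourth, the FAS is itself conditional. It needs a reading after dispensing and nothing is imputed, so a subject with no Week 1 value supplies none to either set. This limits the remedy to measured subjects whom PP removes.

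**Conclusion.** The point holds in a conditional form. Primary inference is on PP, and nothing visible ties either claim to the FAS. Bias toward noninferiority arises only if a DEP criterion is related to lens performance; otherwise the error stays near nominal. Under the assumed control rates, with the true difference at the margin and 10 to 30% of failures excluded equally in both arms, the secondary false noninferiority rate is about 4 to 9% at 96:48 instead of 2.7%. The test-only figures of 5 to 16% are an upper bound for those fractions, not an expectation, since masked criteria would not remove failures from one arm by design. Nothing in the documents supports a particular exclusion fraction. The gap is worth closing because the protection is cheap.

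**What to change.** In SAP section 4, state (or confirm, if the redacted text already says so) that noninferiority is claimed for each endpoint only if the confidence limit meets the margin in both the PP set and the FAS, and that no claim is made if they disagree. PP can remain the first-listed analysis. Report PP exclusions by lens and by reason, unless the redacted part of SAP section 3 already provides this.

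The cost is one sentence, one rerun of the models on a set already defined, and a slightly harder success rule. With no true difference and random PP exclusions of 5% and 10%, secondary power at 96:48 falls as follows:
- rate 0.90: from 0.521 to 0.492 and from 0.501 to 0.464
- rate 0.95: from 0.745 to 0.731 and from 0.726 to 0.707

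That is about 1 to 4 points. At 192:96 the loss is about 0.4 to 2 points. The primary endpoint loses almost nothing at an assumed SD of 0.10, where the interval half-width is 1.96 × 0.10 × sqrt(1/96 + 1/48) = 0.035 against a margin of 0.10.
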